1. DOCUMENT HISTORY

Date	Description	Protocol Version
19 August 2016	Version 1	Final version 1: 12 November 2015
14 May 2018	Amendment 1: amendment of the SAP to better match with the planned analyses described in the protocol and the approved TFL for the Y10 and re-vaccination part (dated 26MAR2018). None of those modifications are major changes to planned analysis	Final version 1: 12 November 2015

2. STUDY DESIGN

The following group names will be used for the statistical analyses:

Group order in tables	Group label in tables	Group definition for footnote	Pooled Groups label in tables
1	gE501B	50 µg gE/AS01 _B	gE501B

The following subgroup names will be used for the statistical analyses by age stratum:

Sub-group order in tables	Sub-group label in tables	Sub-group definition for footnote
1	60-69 YOA	60-69 years old subjects at time of initial vaccination in study ZOSTER-003
2	≥70 YOA	Over 70 years old subjects at time of initial vaccination in study ZOSTER-003

3. OBJECTIVES

3.1. Primary objective

- To evaluate persistence of humoral and cell-mediated immune responses overall at Months 108 and 120 post first dose of initial vaccination course in study ZOSTER-003.

Refer to Section 4.1 for the definition of the primary endpoints.

3.2. Secondary objectives

For the persistence phase Months 108 and 120 post first dose of initial vaccination in study ZOSTER-003:

- To evaluate the persistence of humoral and cell-mediated immune responses within each age cohort (60-69 YOA and ≥ 70 YOA at the time of the initial vaccination) at Months 108 and 120 post first dose of initial vaccination course.
- To evaluate the safety of the study vaccine from Months 108 to Months 120 post first dose of initial vaccination course.

For the re-vaccination phase:

- To evaluate humoral and cell-mediated immune responses to a two dose re-vaccination course at one month after each dose (Months 121 and 123) and 12 months after last dose (Month 134) when administered 10 years after the initial vaccination course.
- To evaluate the reactogenicity and safety of the study vaccine after re-vaccination with two additional doses.

Refer to Section [4.2](#) for the definition of the secondary endpoints.

4. ENDPOINTS

4.1. Primary endpoints

- Antigen-specific antibody (Ab) concentrations at Months 108 and 120 post first dose of initial vaccination course in study ZOSTER-003.
 - Anti-gE Ab concentrations as determined by ELISA at Months 108 and 120.
- Cell-Mediated Immunity (CMI) in terms of frequencies of antigen-specific CD4+T-cells at Months 108 and 120 post first dose of initial vaccination course in study ZOSTER-003.
 - Frequencies of CD4+T cells with antigen-specific Interferon gamma (IFN- γ) and/or Interleukin-2 (IL-2) and/or Tumour Necrosis Factor alpha (TNF- α) and/or CD40 Ligand (CD40L) secretion/expression to gE as determined by Intracellular Cytokine Staining (ICS) at Months 108 and 120.

4.2. Secondary endpoints

For the follow-up of persistence phase Months 108 and 120 post first dose of initial vaccination course in study ZOSTER-003:

- Antigen-specific antibody (Ab) concentrations within each age cohort (60-69 YOA and ≥ 70 YOA at the time of initial vaccination) at persistence Months 108 and 120.
 - Anti-gE Ab concentrations as determined by ELISA at Months 108 and 120.
- Cell-Mediated Immunity (CMI) in terms of frequencies of antigen-specific CD4+T-cells within each age cohort (60-69 YOA and ≥ 70 YOA at the time of initial vaccination) at persistence Months 108 and 120 post first dose of initial vaccination course.
 - Frequencies of CD4+T cells with antigen-specific Interferon gamma (IFN- γ) and/or Interleukin-2 (IL-2) and/or Tumour Necrosis Factor alpha (TNF- α) and/or CD40 Ligand (CD40L) secretion/expression to gE as determined by Intracellular Cytokine Staining (ICS) at Months 108 and 120.
- Serious Adverse events:
 - Occurrence of all serious adverse events (SAEs) related to study participation or to a concurrent GSK medication/vaccine (including HZ/su administered during the ZOSTER-003 study) between Months 108 and 120.

For the re-vaccination phase:

- Antigen-specific antibody (Ab) concentrations post re-vaccination.
 - Anti-gE antibody concentrations as determined by ELISA in all subjects at one month after each vaccine dose (Months 121 and 123) and 12 months after last dose (Month 134).
- Cell-Mediated Immunity (CMI) in terms of frequencies of antigen-specific CD4+T-cells at one month after each vaccine dose (Months 121 and 123) and 12 months after last dose (Month 134).
 - Frequencies of CD4+T cells with antigen-specific Interferon gamma (IFN- γ) and/or Interleukin-2 (IL-2) and/or Tumour Necrosis Factor alpha (TNF- α) and/or CD40 Ligand (CD40L) secretion/expression to gE as determined by Intracellular Cytokine Staining (ICS) at Months 121, 123 and 134.
- Solicited local and general symptoms:
 - Occurrence and intensity of each solicited local symptom within 7 days (Days 0-6) after each vaccination in all subjects;
 - Occurrence, intensity and relationship to vaccination of each solicited general symptom within 7 days (Days 0-6) after each vaccination, in all subjects;
- Unsolicited adverse events (AEs)
 - Occurrence, intensity and relationship to vaccination of unsolicited AEs during 30 days (Days 0-29) after each vaccination, according to the Medical Dictionary for Regulatory Activities (MedDRA) classification in all subjects
- SAEs
 - Occurrence and relationship to vaccination of all SAEs from dose 1 of re-vaccination until study end.
 - Occurrence of any fatal SAEs from dose 1 of re-vaccination until study end.
- Potential immune-mediated diseases (pIMDs)
 - Occurrence and relationship to vaccination of any pIMDs from dose 1 of re-vaccination until study end in all subjects.

5. STUDY POPULATION

The TVC and ATP cohorts are described in section 10.4 of the protocol. The list of applicable elimination codes for each cohort can be found in the study specific form FORM-BIO-CLIN-9004-05 Criteria for eliminating subjects from the analyses.

Cohort	Elimination codes	Eli Type
ATP cohort for immunogenicity Y9	1040-2500	PR
ATP cohort for immunogenicity Y10	1040-2500	P1
Total Vaccinated cohort for re-vaccination phase	1030	MA
ATP cohort for analysis for immunogenicity after re-vaccination	1030-2500	MA
ATP cohort for immunogenicity Y11	1040-2500	FU

6. STATISTICAL METHODS

6.1. Analysis of demographics/baseline characteristics

The analysis of demography for the persistence phase at Month 108 and Month 120 post first dose of initial vaccination course will be performed on the Total enrolled cohort, the ATP cohort for immunogenicity Y9 and ATP cohort for immunogenicity Y10 respectively.

- Demographic characteristics (age at first initial vaccination dose, gender, geographic ancestry, race and ethnicity), cohort description and withdrawal status will be summarized overall.
- The mean age (plus range and standard deviation) as a whole and stratified by age category at dose 1 of initial vaccination in ZOSTER-003 will be calculated.
- The distribution of subjects enrolled among the study sites will be tabulated.
- Frequency tables will be generated for categorical variables such as gender.
- Mean, median and standard error will be provided for continuous data such as age.

The analysis of demography for the re-vaccination phase will be performed on the total vaccinated cohort (TVC) for re-vaccination phase, ATP cohort for immunogenicity after re-vaccination and ATP cohort for immunogenicity Y11.

- Demographic characteristics (age at first re-vaccination dose, gender, geographic ancestry, race and ethnicity), cohort description and withdrawal status will be summarized overall.
- The mean age at first re-vaccination dose (plus range and standard deviation) as a whole and stratified by age category at dose 1 of initial vaccination in ZOSTER-003 will be calculated.
- The distribution of subjects vaccinated among the study sites will be tabulated.
- Frequency tables will be generated for categorical variables such as gender.
- Mean, median and standard error will be provided for continuous data such as age.

6.2. Analysis of immunogenicity

6.2.1. Assessment of follow-up of persistence phase Months 108 and 120 after initial vaccination course.

The analysis for the persistence phase at Month 108 and Month 120 after initial vaccination course will be performed on the ATP cohort for immunogenicity at Y9 and ATP cohort for immunogenicity at Y10. If, the percentage of subjects with serological results excluded from the ATP cohort for analysis of persistence is 5% or more, a second analysis based on the total enrolled cohort will be performed to complement the ATP analysis. All analyses will be performed overall and by age category at dose 1 of initial vaccination in ZOSTER-003 if the number of subjects is sufficient in each stratum.

The exploratory analysis of modelling the persistence of immune response (humoral and cellular) after initial vaccination will be performed on subjects who received two doses of HZ/su vaccine in ZOSTER-003.

Humoral Immune response

- At each timepoint that a blood sample is available (at Months 0, 3, 12, 24, 36, 48, 60, 72, 108 and 120) post initial vaccination, the following parameters will be tabulated overall, and some by age category at dose 1 of initial vaccination in ZOSTER-003:
 - Geometric mean concentrations (GMCs) of anti-gE Ab with 95% confidence interval (CIs);
 - Anti-gE seropositivity rates with exact 95% confidence interval (CIs);
 - Descriptive statistics on Anti-gE antibody concentrations (mean, standard deviation, min, Q1, median, Q3, max)
 - Vaccine response rates for anti-gE antibody concentrations
 - Descriptive statistics of the fold increase over pre-vaccination in the initial study at months 3, 12, 24, 36, 48, 60, 72, 108 and 120 (mean, standard deviation, min, Q1, median, Q3, max).
 - Distribution of the fold over pre-vaccination in the initial study at months 3, 12, 24, 36, 48, 60, 72, 108 and 120
 - Mean Geometric Increase (MGI), ie geometric mean of the ratio Post-vaccination at months 3, 12, 24, 36, 48, 60, 72, 108 and 120 over pre-vaccination in the initial study, with 95% CI.
- The distribution of antibody titers at Months 48, 60, 72, 108 and 120 will be presented using reverse cumulative curves.

CMI response

- Descriptive statistics (N, mean, SD, min, Q1, median, Q3, max) for the following parameters will be tabulated at Months 0, 3, 12, 24, 36, 48, 60, 72, 108 and 120 post first dose of initial vaccination overall and some by age category at dose 1 of initial vaccination in ZOSTER-003 [60-69, ≥ 70 YOA]:
 - the frequency of gE specific CD4+T-cells secreting at least 2 activation markers (among IFN- γ , IL-2, TNF- α , CD40L)
 - the frequency of CD4+T-cells following induction with gE secreting at least two activation markers (among IFN- γ , IL-2, TNF- α , CD40L)
 - the fold increase over pre-vaccination in the frequency of gE-specific CD4(2+) T-cells
 - the fold increase over pre-vaccination in the frequency of CD4(2+) T-cells following induction with gE
- Vaccine response rates of frequency of gE-specific CD4(2+) T-cells up to Month 120 post-vaccination will be tabulated with 95% CI

Exploratory analysis

- A piece-wise linear mixed model, power law model and modified power law model [David, 2009] for repeated measurements (all data available from month 0, 3, 12, 24, 36, 48, 60, 72, 108 and 120 post first dose of initial vaccination) will be used to model over time
 - the frequency of gE specific CD4+T-cells secreting at least 2 activation markers (among IFN- γ , IL-2, TNF- α , CD40L)
 - the frequency of CD4+T-cells following induction with gE secreting at least 2 activation markers (among IFN- γ , IL-2, TNF- α , CD40L)
 - the gE antibody concentrations
- The three models based on data up to M120 will be presented graphically. Models based on data up to M108 and on data up to M120 will be presented side by side.

6.2.2. Assessment of re-vaccination phase

The analysis of re-vaccination phase will be based on the ATP cohort for analysis of immunogenicity after re-vaccination. If, the percentage of vaccinated subjects with serological results excluded from the ATP cohort for analysis of immunogenicity after re-vaccination is 5% or more, a second analysis based on the TVC will be performed to complement the ATP analysis.

All analyses will be performed overall and by age category at dose 1 of initial vaccination in ZOSTER-003 (60-69, ≥ 70 YOA) if the number of subjects is sufficient in each stratum.

Humoral Immune response

- At each timepoint that a blood sample is available (at Months 120, 121 and 123) post-re-vaccination, the following parameters will be tabulated overall and some by age category at dose 1 of initial vaccination in ZOSTER-003 (60-69, ≥ 70 YOA):
 - GMCs of anti-gE Ab with 95% confidence interval (CIs);
 - Anti-gE seropositivity rates with exact 95% confidence interval (CIs);
 - Vaccine response rates [post re-vaccination (M121 and M123) over pre-vaccination in the initial ZOSTER-003 study] with 95% confidence interval (CIs);
 - MGI (geometric mean of the ratio) Post Month 1 (Month 121) and post Month 3 (Month 123) post re-vaccination (current study) over Pre-re-vaccination (Month 120), with 95% CI;
 - Descriptive statistics of the fold increase over pre-re-vaccination at months 121 and 123 (mean, standard deviation, min, Q1, median, Q3, max).
 - Distribution of the fold increase over pre-re-vaccination at months 121 and 123
 - MGI (geometric mean of the ratio) Post Month 1 (Month 121) and post Month 3 (Month 123) post re-vaccination (current study) over pre-vaccination in the initial ZOSTER-003 study, with 95% CI;
- The distribution of antibody titers at Months 120, 121 and 123 will be presented using reverse cumulative curves.

CMI response

- Descriptive statistics (N, mean, SD, min, Q1, median, Q3, max) for the following parameters will be tabulated at Months 120, 121 and 123 overall and some by age category at dose 1 of initial vaccination in ZOSTER-003 [60-69, \geq 70 YOA]:
 - the frequency of gE specific CD4+T-cells secreting at least 2 activation markers (among IFN- γ , IL-2, TNF- α , CD40L)
 - the frequency of CD4+ T-cells following induction with gE secreting at least 2 activation markers (among IFN- γ , IL-2, TNF- α , CD40L)
 - the fold increase over pre-re-vaccination in the frequency of gE specific CD4[2+] T-cells at months 121 and 123
 - the fold increase over pre-re-vaccination in the frequency of CD4[2+] T-cells following induction with gE at months 121 and 123
 - the fold increase over pre-vaccination in the initial ZOSTER-003 study in the frequency of gE specific CD4[2+] T-cells at months 121 and 123
 - the fold increase over pre-vaccination in the initial ZOSTER-003 study in the frequency of CD4[2+] T-cells following induction with gE at months 121 and 123
- Vaccine response rates of frequency of gE-specific CD4(2+) T-cells at Months 121 and 123 over pre-vaccination in the initial ZOSTER-003 study will be tabulated with 95% CI.

6.2.3. Assessment of persistence after re-vaccination

Persistence data will be analyzed at Month 134 timepoint after re-vaccination (i.e. 12 months after last dose of re-vaccination).

The analysis of antibody persistence after re-vaccination at Month 134 will be based on the ATP cohort for analysis of immunogenicity at Y11. If the percentage of subjects who come back for this follow-up with serological results excluded from the ATP cohort is higher than 5%, a second analysis based on the TVC for revaccination course will be performed to complement the ATP analysis.

Humoral immune response:

- If a blood sample is available at Month 120, 121, 123 and 134, the following parameters (with 95% CIs) will be tabulated overall and some by age group (60-69, ≥ 70 YOA at time of initial vaccination in study ZOSTER-003):
 - GMCs of anti-gE Ab with 95% confidence interval (CIs);
 - Anti-gE seropositivity rates with exact 95% confidence interval (CIs);
 - Vaccine response rates [post re-vaccination over pre-vaccination in the initial ZOSTER-003 study] with 95% confidence interval (CIs);
 - MGI (geometric mean of the ratio) post re-vaccination (current study) over Pre-re-vaccination (Month 120), with 95% CI;
 - Descriptive statistics of the fold increase over pre-re-vaccination at months 121, 123 and 134 (mean, standard deviation, min, Q1, median, Q3, max).
 - Distribution of the fold increase over pre-re-vaccination at months 121, 123 and 134
 - MGI (geometric mean of the ratio) post re-vaccination (current study) over pre-vaccination in the initial ZOSTER-003 study, with 95% CI;
- The distribution of antibody titers at Months 121, 123 and 134 will be presented using reverse cumulative curves.

CMI response:

- Descriptive statistics (N, mean, SD, min, Q1, median, Q3, max) for the following parameters will be tabulated at Months 120, 121, 123 and 134 overall and some by age category at dose 1 of initial vaccination in ZOSTER-003 [60-69, ≥ 70 YOA]:
 - the frequency of gE specific CD4+T-cells secreting at least 2 activation markers (among IFN- γ , IL-2, TNF- α , CD40L)
 - the frequency of CD4+ T-cells following induction with gE secreting at least 2 activation markers (among IFN- γ , IL-2, TNF- α , CD40L)
 - the fold increase over pre-re-vaccination in the frequency of gE specific CD4[2+] T-cells at months 121, 123 and 134
 - the fold increase over pre-re-vaccination in the frequency of CD4[2+] T-cells following induction with gE at months 121, 123 and 134
 - the fold increase over pre-vaccination in the initial ZOSTER-003 study in the frequency of gE specific CD4[2+] T-cells at months 121, 123 and 134
 - the fold increase over pre-vaccination in the initial ZOSTER-003 study in the frequency of CD4[2+] T-cells following induction with gE at months 121, 123 and 134
- Vaccine response rates of frequency of gE-specific CD4(2+) T-cells at Months 121, 123 and 134 over pre-vaccination in the initial ZOSTER-003 study will be tabulated with 95% CI.

6.3. Analysis of safety and reactogenicity**6.3.1. Persistence phase**

Analyses in the follow-up of persistence phase will be performed on the Total enrolled cohort.

Description of SAEs and HZ cases will be provided.

6.3.2. Re-vaccination phase

The primary analysis for safety will be based on the TVC for re-vaccination course.

Safety and reactogenicity analyses will be performed overall and by age category at dose 1 of initial vaccination in ZOSTER-003 [60-69, ≥ 70 YOA] if the number of subjects is sufficient in each stratum.

When appropriate, tabulations will be presented overall and by time of occurrence relative to last vaccination (e.g., using windows such as Days 0-6, Days 0-29 and more than 30 days post-vaccination).

The results for the analysis of safety will be tabulated as follows:

- The number and percentage of subjects with at least one local solicited AE, with at least one general solicited AE and with any solicited AE during the 7-day follow-up period with exact 95% CIs after each vaccine dose and overall will be provided; the same tabulation will be performed for grade 3 symptoms and for solicited and unsolicited symptoms.
- The percentage of subjects reporting each individual solicited local and general AE during the solicited 7-day follow-up period will be tabulated with exact 95% CI;
- For all solicited symptoms, the same tabulation will be performed for grade 3 solicited AEs and for solicited general AEs with relationship to vaccination;
- Summary of temperature value by half degree increment reported during the 7-day (Days 0-6) post-vaccination period following each dose and subjects
- Number of days with solicited symptoms will be tabulated
- The proportion of subjects/doses with at least one report of unsolicited AE classified by the MedDRA preferred terms and reported up to 30 days after each vaccination will be tabulated with exact 95% CI;
- The same tabulations will be performed for grade 3 unsolicited AEs (not including SAEs) and for unsolicited AEs with a relationship to vaccination. The proportion of AEs resulting in a medically attended visit will also be tabulated;
- Number and percentage of subjects with pIMDs classified by the MedDRA preferred terms will be tabulated and described in detail; the same for SAEs.
- SAEs and withdrawal due to AE(s) will be described in detail.
- Potential and confirmed HZ cases identified during the study will be listed.

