10.8.2. Re-vaccination phase

Analyses post the re-vaccination phase will be performed on the Total vaccinated cohort.

All safety analyses might be performed by age stratum (60-69 and \geq 70 YOA at the time of initial vaccination as in ZOSTER-003 study) when the size of the category is considered meaningful.

- The percentage of subjects with at least one local solicited AE, with at least one general solicited AE and with any solicited AEs during the solicited 7-day follow-up period will be tabulated with exact 95% CI after each vaccine dose and overall. The same tabulation will be performed for grade 3;
- The percentage of subjects reporting each individual solicited local and general AE during the solicited 7-day follow-up period will be tabulated with exact 95% CI. For all solicited symptoms, the same tabulation will be performed for grade 3 solicited AEs and for solicited general AEs with relationship to vaccination ;
- The percentage of subjects reporting temperature by half degree ($^{\circ}$ C) cumulative increments. Similar tabulations will be performed for any fever with a causal relationship to vaccination and for any fever resulting in a medically attended visit ;
- The proportion of subjects with at least one report of unsolicited AE classified by the MedDRA Preferred Terms and reported up to 30 days after each vaccination will be tabulated with exact 95% CI;
- The same tabulation will be performed for grade 3 unsolicited AEs and for unsolicited AEs with a relationship to vaccination. The proportion of AEs resulting in a medically attended visit will also be tabulated ;
- Total number/percentages of doses (per dose and overall) followed by AEs will be tabulated;
- Number of subjects with pIMDs will be tabulated;
- All SAEs will be tabulated;
- SAEs related to vaccine will be tabulated and described;
- SAEs related to study participation or to GSK concomitant medication/vaccine will be tabulated and described;
- Adverse events (AEs)/SAEs leading to withdrawal from the study will be tabulated;
- Intercurrent medical conditions will be tabulated.

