7.1.3. Safety and reactogenicity**7.1.3.1. Counting rule**

The way the percentage of subjects will be derived will depend on the event analyzed (see the following table for details). As a result, the denominator (N) will differ from one table to another.

Event	N used for deriving %	Terminology used in the tables for N
Concomitant medication	All vaccinated subjects	Number of subjects with at least one administered dose
Solicited general symptom	All vaccinated subjects with at least one solicited general symptom documented as either present or absent	For each dose and overall/subject: N= number of subjects with at least one documented dose For overall/dose: N= number of documented doses
Solicited local symptom	All vaccinated subjects with at least one solicited local symptom documented as either present or absent	For each dose and overall/subject: N= number of subjects with at least one documented dose For overall/dose: N= number of documented doses
Unsolicited symptom from day 0 to day X	All vaccinated subjects	Number of subjects with at least one administered dose
SAE	All vaccinated subjects	Number of subjects with at least one administered dose

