7.4. Methodology for computing CI

Unless otherwise mentioned, the confidence intervals will be 2sided 95% CI and calculated according to the following methods:

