7.4.1. Binomial Data

The exact 95% CIs for a proportion within a group will be calculated according to [Clopper, 1934].

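### The SAP's exact 95% CI on the proportion of doses with an unsolicited AE takes no account of two doses per subject, and its dose-level N is undefined

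*SAP*

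**What the plan says.** SAP 6.3.2 (re-vaccination phase) lists "The proportion of subjects/doses with at least one report of unsolicited AE", by MedDRA preferred term, "reported up to 30 days after each vaccination will be tabulated with exact 95% CI". The next bullet extends the same tabulations to grade 3 unsolicited AEs (excluding SAEs) and to vaccine-related unsolicited AEs.

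SAP 7.4 states that, unless otherwise mentioned, "the confidence intervals will be 2sided 95% CI". For binomial data SAP 7.4.1 gives one rule: "The exact 95% CIs for a proportion within a group will be calculated according to" Clopper-Pearson. It has no separate rule for a denominator of doses.

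The counting rule in SAP 7.1.3.1 has two kinds of N, but only in the rows for solicited general and solicited local symptoms. These are "For each dose and overall/subject: N= number of subjects with at least one documented dose" and "For overall/dose: N= number of documented doses". The row for unsolicited symptoms gives N in vaccinated subjects only.

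Protocol 10.8.2 puts the exact CI for unsolicited AEs on the proportion of subjects. A separate bullet reads "Total number/percentages of doses (per dose and overall) followed by AEs will be tabulated", with no interval. All subjects are to receive two doses (Protocol 1.2.2), and about 100 subjects are expected (Protocol section 3, Table 1).

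**The concern.** Clopper-Pearson treats each unit in the denominator as an independent Bernoulli trial. When doses are pooled over the course, one subject supplies two units. A person who reports an event after the first dose may well be more likely to report one after the second, and then the pooled proportion varies more than the binomial formula allows. The interval is labelled 95% but covers less.

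In a single-group, descriptive study the estimate and its interval are the result, and reactogenicity and safety after re-vaccination is a secondary objective. An interval that looks more precise than the data allow would be read at face value. Separately, a programmer cannot tell from the SAP which dose count to use for unsolicited AEs, because SAP 6.3.2 asks for doses and SAP 7.1.3.1 provides only subjects.

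**Working it through.** The documents state no event rate, within-subject correlation or interval width, so there is no planned figure to reproduce.

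**Inputs.** From the documents: two doses per subject, about 100 subjects, two-sided 95% Clopper-Pearson. Assumed: n = 60 as a lower turnout alongside n = 100; the same event rate p after each dose; within-subject correlation rho from 0 to 0.7.

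**Variance.** For n subjects with two doses each, the variance of the pooled proportion is p(1 - p)(1 + rho) / (2n). The binomial formula omits (1 + rho). The standard error is therefore understated by sqrt(1 + rho), which is 1.14 at rho 0.3 and 1.22 at rho 0.5.

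**Width, n = 100, p = 0.30.** With 60 events in 200 doses, Clopper-Pearson gives 23.7% to 36.9%, a width of 13.1 points. The effective number of doses is 200 / (1 + rho).
- rho 0.3: 200 / 1.3 = 153.8, width 15.0 points.
- rho 0.5: 200 / 1.5 = 133.3, width 16.2 points.

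**Coverage.** For one subject:
- P(event after both doses) = p^2 + rho p(1 - p)
- P(event after exactly one dose) = 2[p - P(both)]
- P(none) = 1 minus the other two.

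For p = 0.30 and rho = 0.3 these are 0.09 + 0.3 x 0.21 = 0.153, 2 x 0.147 = 0.294, and 0.553. Convolving n such subjects gives the exact distribution of the event count among 2n doses. Coverage is the total probability of the counts whose Clopper-Pearson interval contains p. The ranges below are over n = 60 and n = 100.

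| rho | p = 20%, 40%, 70% | p = 1%, 2%, 3%, 5% |
|---|---|---|
| 0 | 95.5-96.4% | 96.2-99.3% |
| 0.1 | 94.4-95.5% | 95.3-98.9% |
| 0.2 | 93.3-94.4% | 94.2-98.6% |
| 0.3 | 92.1-93.4% | 93.1-98.3% |
| 0.5 | 89.8-91.3% | 90.5-97.7% |
| 0.7 | 87.5-89.2% | 87.2-97.3% |

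**Two boundary checks, n = 100.** With rho = 0 and rates of 70% and 30% after the two doses, coverage is 97.5%. With rho = -0.2 and p = 30% or 50%, it is 97.5-97.8%. The shortfall therefore needs positive correlation.

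**The case against.** Three arguments on the other side carry weight.

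First, no single place in the SAP pairs a denominator of documented doses with an exact CI. The dose-level N belongs to solicited symptoms, and the SAP 6.3.2 bullets that put CIs on solicited AEs speak of percentages of subjects. The bullet that mentions doses concerns unsolicited AEs, whose N is given in subjects. A reader might infer that every pooled-dose row for solicited symptoms will carry a Clopper-Pearson interval on documented doses; the SAP does not say so. This narrows the point to unsolicited AEs but does not remove it. The bullet still asks for a CI on a proportion of doses, and any pooled dose count has two units per subject.

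Second, under-coverage is not automatic. Clopper-Pearson is conservative enough to stay near 95% up to rho of about 0.1. The bullet is classified by preferred term, and single terms may be rare. At rates of 1-5%, coverage is at least 95.3% at rho 0.1 and at least 93.1% at rho 0.3. This stands as a limit on the size, although at rho 0.5 even those rates can give 90.5%.

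Third, the analyses are descriptive and no test, comparison or stopping rule uses these intervals. The per-dose and overall/subject rows serve the safety objective and have one observation per subject. This stands too: what is affected is a supplementary summary.

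**Conclusion.** The point holds in a limited form. As written, the SAP asks for an exact binomial interval on a proportion of doses, makes no allowance for two doses from one person, and does not define that denominator for unsolicited AEs. If a subject's two outcomes are positively correlated, a nominal 95% interval on pooled doses covers about 92-93% at rho 0.3 and 90-91% at rho 0.5, for rates of 20-70% and 60 or 100 subjects. At rho of about 0.1 the loss is negligible, and for rare terms there may be none. Positive correlation is plausible when the same vaccine is given twice to the same person, but the documents give no value for it and no event rate.

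A reader might go further and conclude that the trial's safety intervals are too narrow in general. The documents do not support that: intervals per dose and per subject are valid, and the protocol itself plans no interval on doses. No study conclusion is shown to depend on the affected rows. The change is still worth making, because it is cheap and brings the SAP back to the protocol.

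**What to change.** Three edits to the SAP:

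- **7.4.1:** state that Clopper-Pearson applies to rows with one observation per subject, that is, the per-dose and overall/subject rows.
- **6.3.2 and 7.1.3.1:** define the dose-level N for unsolicited AEs and make the two sections agree on whether subjects, doses or both are tabulated.
- **Any pooled overall/dose row, including the grade 3 and vaccine-related tables:** either show n and % without a CI, as in Protocol 10.8.2, or give a 95% CI with the subject as the cluster (for example a GEE logit interval with robust variance). The first option is simpler and also avoids fitting a model to terms with no or very few events.

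The cost is a few sentences and a small programming change, with no new data and no change to study conduct. The downside is that these supplementary intervals disappear or become somewhat wider.
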